#### **4.4.2 Handling of Withdrawals:**

If a subject is withdrawn from participation in the study at any time at his or her request, at the IRB or Principal Investigator's discretion, the reason(s) for discontinuation shall be documented thoroughly in the source documents and subject's case file. If a subject is discontinued because of an adverse event, this event will be followed until it is resolved or the subject is clinically stable and will also be documented in the source documents and the subject's case file.

### **Study Procedures**

#### **5.1 Design Team Procedures:**

This intervention adaptation aim will involve three phases: brainstorming, conceptualization, and creation:

*During the brainstorming (meeting #1):* the design team will review the mixed-methods data obtained during aim 2 of the study, which sought to gain detailed knowledge about HIV clinic patients' perception of their own CVD risk and the HIV clinic's role in CVD risk reduction. The following topics will be discussed: perception of CVD risk (perceived susceptibility), provider accessibility (perceived barriers), provider prioritization of CVD risk management (perceived barriers), and interventions likely to motivate risk reducing behaviors (perceived benefits and cue to actions). The team will discuss these findings and brainstorm ideas to refine the SWOBI intervention in response to the data. Possible targets for adaptation include a) targeting the staff training to include relevant aspects of perceived risk into the care coordination and adherence support; (b) developing and tailoring staff training to facilitate acceptance, uptake, and effectiveness; and (c) helping us to quickly identify and troubleshoot any problems with the implementation of the intervention.

*During the conceptualization phase (meeting #2):* the team will evaluate advantages and disadvantages of ideas generated during the brainstorming phase, and the educational material developed ahead of this meeting. The team will then develop concrete changes to the intervention. The feasibility of each of the discussed intervention modification will be discussed and finalized into the intervention by the study PI.

[figure not shown]
*During the creation phase (meeting #3):* the team will be involved in the creation of refined manuals of procedures and education materials. After the feasibility testing is completed, the design team will meet for a final time to discuss feasibility testing results from meeting #2 and refine the intervention as needed. At this meeting, the design team members who have given consent to participate in a focus group discussion will reflect on the design process.

## **5.2 Pre-trial demonstration**

Prior to the commencement of the trial, we will recruit one clinic patient to participate in a demonstration of the study intervention telephone modules. The purpose of this demonstration is to give the study social worker the opportunity to execute the trial intervention modules and resolve workflow/logistical concerns with the intervention prior to study launch. The demonstration patient will be recruited by personal invitation of the study investigator. They will be consented prior to their participation in the process. The study patient will be expected to participate in no more than three demonstration sessions. They will serve as a mock recipient of the telephone-based intervention. After conclusion of the demo intervention call, the study team will ask the demo participant questions about the acceptability of the telephone call, as well as their perceived strengths and weaknesses of the telephone module. The demonstration participant will be compensated \$50 for each session for a total of \$150.

## **5.3 Study Timeline**

All enrolled patients will complete 4 study visits as outlined in the flow chart below:

## **5.4 Informed Consent**

Each subject will give informed consent, either using a hard copy consent in person or via the e-consent process in REDCap, prior to enrollment into study during the baseline visit. Research coordinator(s) will read, review, and discuss consent forms with all potential participants prior to asking them to sign. If the candidate appears confused or indicates a lack of understanding, the interviewer will attempt to identify the misunderstanding and to explain the form again. Any candidate who still does not comprehend the form will be excluded from the study. We will ask questions to confirm understanding of the material covered in the consent procedure, both open ended (e.g. "Could you tell me what's going to happen if you enroll in this study?") and closed (e.g. "Is your participation in this study voluntary?"). Persons who understand the consent form and agree to participate in the study will be asked to sign an authorization for the release of medical information to us. Interviewers will witness and date the signed forms and complete the corresponding informed consent checklist to document the participant's understanding of the informed consent process. Consent procedures will take place in a private room or office. Consent forms will be kept in a locked file cabinet within a locked room.

## **5.5 Data collection**

Data will be collected through the electronic data capture system – REDCap. Patients will have the option of providing e-consent on this platform. Participants will be asked to complete patient reported outcome measures via REDCap at various timepoints throughout the study including: single item health literacy, demographics, adherence, IPAQ physical activity, and perception of risk of heart disease scale. In addition, the clinical research coordinators will collect patient information for: medical chart screen, participant screening, BP and cholesterol medications, physical measurements, and outcomes. Adverse events will also be collected to track and ensure safety of the patient throughout the duration of their participation in the study.

## **5.6 Randomization**

We will conduct a randomized controlled pilot trial of the intervention vs. education control group among 50 PLWH on suppressive ART who have either hypertension or hypercholesterolemia. Control participants will receive general prevention education. The intervention will consist of prevention education plus a 24- week intensive telephone-based, social work administered intervention focused on heart-healthy behaviors.

## **5.7 Control group**

Participants assigned to the control group will receive usual clinical care enhanced with a series of 12 packets of educational handouts delivered to patients every two weeks for 24 weeks. . Educational pamphlets will be delivered on one of six topics on a rotational basis (two rotations over a 6-month study period). The topics to be covered by the educational material are as follows: CVD Knowledge and Risk Perception, Medication Reconciliation, Dietary Assessment and Education, Physical Activity and Weight Management, Smoking Cessation, Stress Management. On enrollment, participants will determine the optimal mode of delivery for the educational material (email, regular mail, or text). All participants in the control and intervention arm will complete the following study assessments: 1) in-office BP obtained by a trained research assistant (0, 6, 12, 18 months) 2) lipid profile (0, 6, 12, 18 months)(the default will be to collect data from lipid profiles done as part of routine clinical care, within 4 weeks of baseline visit; if lipid information is not available or exceeds acceptable time point, lipid panel will be collected by the research staff). 3) 10-year ASCVD risk score (0, 6, 12, 18 months) 4) provider trust and communication survey (0, 6, 12, 18 months).

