### **2.1 Primary Objective**

To assess the effect of a telephone based CVD risk reduction intervention on decreasing systolic blood pressure (SBP) and fasting LDL-c levels from baseline.

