#### **4.3 Subject Recruitment and Screening**

**Pre-screening:** we will use the electronic medical records at our site to identify potential subjects for our study according to the inclusion/exclusion criteria. Potential subjects may also be recommended by providers within the Division of Infectious Diseases based on the inclusion/exclusion criteria. Potential subjects will initially be mailed a recruitment letter signed by his or her primary HIV provider. Potential subjects will have the opportunity to opt out of the study by calling a toll-free number.

In addition to receipt of letters, prospective participants will be approached with the permission of their providers during routinely scheduled clinical encounters, by a member of the study team. During such encounters, the study team will inform participants about the study and the reasons why they are eligible to participate. At that point, the patient will have the option to proceed with a baseline screening visit or not.

This study will also utilize cold-calling recruitment methods. This will include contacting the patients directly if they meet eligibility criteria to enroll them into this study. Research coordinator(s) will refer to patients' electronic medical records (EMR) to confirm that the patient(s) have not opted out from being contacted for research studies.

**Screening:** A research coordinator will contact all subjects who do not opt out. Following a telephone script, the research assistant will describe the study in detail, ensure the patient is eligible and willing to participate, and schedule a baseline study visit at the next clinical visit with an HIV provider where they will be enrolled following the informed consent process described below in section 5.1.

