## **5.8 Study Intervention**

In addition to the educational material delivered to the control arm participants, participants randomized to the intervention arm will receive a 24-week telephone-based intervention, customized for the delivery to PLWH by social workers (SW). Participants will be contacted every 2 weeks for a total of 12 calls in the 24-week period by the study social worker. During each call, the participant will have the chance to select a module from 6 modules in a rotating fashion on topics relevant to CVD risk (Table 2). Once a module is chosen, it can only be chosen once more for the duration of the study period. Each telephone session will involve the study SW providing education on the selected module to promote improved CVD health. For the diet, physical activity, and overview of CVD risk factors modules, there will be a low and high literacy version. At baseline the coordinator will assess whether the participant should be low or high literacy based on their discussions. The coordinator will then relay this assessment when notifying the social worker that the participant has been randomized to intervention. During the

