first module, the social worker will make a secondary assessment of the participant's health literacy level. The social worker will have the final decision as to which version of the module the participants will receive. During the call, the social worker will follow the prompts of a telephone script. As part of the intervention, the SW will incorporate MI techniques at different times during the phone call based on the direction of the conversation. Towards the end of each call, the participant will have the option to review any or all of the corresponding educational materials relevant to the module. Each of these calls will take between 30-45 minutes to administer. At the conclusion of the study telephone visit, participants will be delivered a package of educational pamphlets similar to those administered to participants in the control arm. Like the control arm, a total of 12 packets will be delivered to intervention participants via their method of choice. Since this pilot study seeks to determine the independent effect of the SW-based intervention, SWs will be instructed not to feedback on study-related telephone interactions to the participant's provider. This will be facilitated by the physical separation between the SW offices and the provider work area. Recruitment efforts will also be tailored to inform providers about the study with the minimal amount of details on the intervention available to avoid undue influence on their practice patterns.

All study follow up visits will be conducted within a +/- 21 day window.

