### *Blood Pressure*

The participants will have a high risk for CVD and thus many will be prescribed hypertension medications by their health care provider at the outset of the study. It is likely that as a result of increased monitoring, we will detect more episodes of abnormal BP values. BP will be measured at each follow up visit. Participants will have access to their regular providers as well as the study investigator designated as the clinical contact for the study: [name] (infectious disease physician; Duke Health). An average SBP at any study visit  $>180$  mm Hg and/or diastolic is  $>110$  mm Hg will be considered an alert value and will trigger assessment by the study clinician. Additionally, an average BP at any study visit that is  $<90$  systolic or  $<40$  diastolic would also be considered an alert value and would trigger an assessment by the study clinician.

Participants who have an alert BP reading during study visits will be directly assessed for cardiovascular symptoms during the visit. Once an alert value has been confirmed, the participant will be triaged according to follow-up recommendations from Joint National Committee Recommendations (JNC 8). If at any time, participants have symptoms of acute end organ damage (i.e. current chest pain, dyspnea at rest, new onset of blurry vision, or new neurological deficits consistent with a stroke) in the context of an elevated BP measurement (SBP  $>180$ , and/or DBP  $>110$ ), participants will be asked to contact the clinician and will be advised and assisted in seeking emergency medical care.

For participants in the intervention group whose average SBP  $>180$  and DBP  $>110$  or SBP  $<90$  or DBP  $<40$  but are without acute symptoms, the participant's primary provider will be notified. Follow up contact with the study staff will occur within one week. All abnormal blood pressure results will be communicated to the clinic director at each site who will be an integral part of triage and ensuring follow up. The SW will then generate a note to be entered into the electronic medical record and will communicate directly with the subject's PCP.

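### No masking of the follow-up blood pressure assessor is described, and the protocol does not separate that person from the coordinators who know the allocation

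*Combined protocol and SAP*

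**What the plan says.** The primary objective (section 2.1) is the effect of the intervention "on decreasing systolic blood pressure (SBP) and fasting LDL-c levels from baseline".

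Section 5.7 assigns the measurement, for both arms and at 0, 6, 12 and 18 months: "in-office BP obtained by a trained research assistant".

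Section 5.5 assigns data collection: "the clinical research coordinators will collect patient information for: medical chart screen, participant screening, BP and cholesterol medications, physical measurements, and outcomes".

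Section 5.8 shows who knows the allocation. After describing the coordinator's baseline literacy assessment, it says: "The coordinator will then relay this assessment when notifying the social worker that the participant has been randomized to intervention".

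On how SBP is read, the Blood Pressure part of section 7.2 sets its alert threshold on "An average SBP at any study visit", which implies more than one reading. The number of readings, the device and the technique are not given.

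The protocol does try to limit some outside influence. Section 5.8 tells social workers not to report the calls back to providers, and says that recruitment will "inform providers about the study with the minimal amount of details on the intervention available to avoid undue influence on their practice patterns". No corresponding step covers the people who measure outcomes.

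**The concern.** Participants in a telephone-counselling trial know their arm. The person taking the blood pressure need not, and the reading procedure can be fixed in advance. The protocol does neither. An observer who knows the arm can affect an office reading through the decision to repeat it, through rounding, or through the choice of which value to record.

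This matters because section 6.1 gives the purpose of the pilot as determining the effect size, so that later trials can be powered. A difference between arms that comes from measurement enters the arm-by-time interaction in section 6.2, and from there the effect size carried forward. The analysis cannot separate it from a treatment effect.

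**Working it through.** **1. Who measures, and who knows the arm.** Set side by side:

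- Section 5.7: a research assistant takes the office blood pressure.
- Section 5.5: the coordinators collect physical measurements and outcomes.
- Section 5.8: the coordinator passes the allocation to the social worker, so at least one coordinator knows it.
- Section 4.3: a research coordinator contacts potential subjects, and the next sentence continues the same call with another title: "Following a telephone script, the research assistant will describe the study in detail". The two titles are not used there as distinct roles.

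Two further places could reveal the arm around a visit. In section 7.2, one notification step for alert readings is written for the intervention group, so whoever acts on it must know the arm. Section 5.11 allows the post-intervention interview at the 6-month visit, when the end-of-intervention blood pressure is also due, and the interview guide asks about the interventionist.

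The text therefore does not separate the assessor from staff who know the allocation. It does not show that one person does both.

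**2. Which measurements are exposed.** These are the SBP readings taken after randomisation (6, 12 and 18 months). A baseline reading taken before randomisation would not be affected, but the order is not stated. LDL-c comes from a laboratory.

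**3. The plan's own figures (section 6.1).**

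- Effect size: 7.6 / 15 = 0.507, stated as 0.51. Reproduced.
- Analysed sample: 50 × (1 − 0.20) = 40, or 20 per arm. Reproduced.
- Cut-off: 0.3 × 15 = 4.5 mmHg.

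No alpha or power is stated. Two-sided 5% is assumed below, and 15 mmHg is taken as the SD of the quantity compared between arms.

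**4. Illustration with an assumed bias b.** The documents give no value for b. It is taken as a constant difference between arms in the favourable direction, with no true effect.

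- Standard error: 15 × √(2/20) = 4.74 mmHg.
- Shift: b / 4.74, which is 0.42 for b = 2.
- False-positive rates come from the noncentral t distribution with 38 df. The chance of reaching 4.5 mmHg uses the normal approximation, 1 − Φ((4.5 − b)/4.74).

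| b (mmHg) | b / 7.6 | favourable tail | two-sided | observed effect reaches 0.3 |
|---|---|---|---|---|
| 0 | 0% | 2.5% | 5.0% | 17% |
| 1 | 13% | 4.0% | 5.5% | 23% |
| 2 | 26% | 6.1% | 7.0% | 30% |
| 3 | 39% | 9.0% | 9.5% | 38% |

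**5. Effect on a later trial (80% power, normal approximation).** The sample size per arm is 2 × (15 × (1.96 + 0.84) / d)². For d = 7.6 this is 62.

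- If an observed 7.6 contained 2 mmHg of bias, the true difference would be 5.6. The trial would need 113 per arm, and 62 per arm would give about 55% power.
- With 3 mmHg of bias the true difference would be 4.6. The trial would need 167 per arm, and 62 per arm would give about 40% power.

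**The case against.** The strongest reply is that the only sentence on who takes the blood pressure names a research assistant, while the person who transmits the allocation is the coordinator. Section 5.5 may mean that coordinators record data in REDCap rather than take the readings, and the change of title in section 4.3 may be loose drafting in one place. This stands in part. A reader might infer that the same person, or settled role, measures SBP and knows the arm; the documents do not establish that. What remains is that they do not separate the two and mask neither.

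It can also be said that the protocol already requires a trained assessor, uses an average for alert values, and may leave device details to a manual not included here. Training and averaging help, but the protocol does not fix how many readings there are, how they are taken, or that all are kept.

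A third reply is that the numbers are assumptions, and that a 2 mmHg bias is under half of one standard error, so sampling error dominates in a trial of this size. That is correct, and the false-positive change is modest. But sampling error is reflected in the confidence interval, whereas a measurement bias is not.

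Finally, the observer is not the only place where bias in SBP can be controlled. The limits in section 5.8 on what reaches providers act on co-intervention. They do not act on measurement.

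**Conclusion.** The point holds in a limited form. No masking of the follow-up blood pressure assessor is described, and that person is not separated from the coordinators who know and transmit the allocation. Post-randomisation office SBP, one of the two primary outcomes, is therefore open to observer bias.

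The size and direction of any bias are unknown. The 2 mmHg case (two-sided false-positive rate from 5% to about 7%) rests on an assumed favourable bias, 20 analysed per arm, SD 15 mmHg and two-sided 5%. For a pilot, the more relevant consequence is that any such bias is carried one-for-one into the effect size used to plan the next trial.

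A reader might also infer that the bias can be removed entirely without extra staff. The documents do not support this. They mention coordinators in the plural and a research assistant but give no headcount, and participants know their arm and can disclose it. The bias can be reduced, and the change is worth making.

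**What to change.** In sections 5.5 and 5.7:

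- State who measures blood pressure at follow-up and whether they know the arm.
- Where existing staffing allows, use a staff member who did not handle that participant's randomisation or the notification to the social worker, and hide the REDCap allocation field from that user.
- In all cases, use an automated device with a prespecified number of readings, enter every reading, and let REDCap compute the mean.
- Take blood pressure before any post-intervention interview held at the same visit, and ask participants not to disclose their arm.

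The cost is protocol wording, REDCap user rights, some rostering and some loss of scheduling flexibility. If only one staff member is available, the fixed automated procedure still applies. The planned sample size and stated effect size do not change.

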## **5.8 Study Intervention**

In addition to the educational material delivered to the control arm participants, participants randomized to the intervention arm will receive a 24-week telephone-based intervention, customized for the delivery to PLWH by social workers (SW). Participants will be contacted every 2 weeks for a total of 12 calls in the 24-week period by the study social worker. During each call, the participant will have the chance to select a module from 6 modules in a rotating fashion on topics relevant to CVD risk (Table 2). Once a module is chosen, it can only be chosen once more for the duration of the study period. Each telephone session will involve the study SW providing education on the selected module to promote improved CVD health. For the diet, physical activity, and overview of CVD risk factors modules, there will be a low and high literacy version. At baseline the coordinator will assess whether the participant should be low or high literacy based on their discussions. The coordinator will then relay this assessment when notifying the social worker that the participant has been randomized to intervention. During the

first module, the social worker will make a secondary assessment of the participant's health literacy level. The social worker will have the final decision as to which version of the module the participants will receive. During the call, the social worker will follow the prompts of a telephone script. As part of the intervention, the SW will incorporate MI techniques at different times during the phone call based on the direction of the conversation. Towards the end of each call, the participant will have the option to review any or all of the corresponding educational materials relevant to the module. Each of these calls will take between 30-45 minutes to administer. At the conclusion of the study telephone visit, participants will be delivered a package of educational pamphlets similar to those administered to participants in the control arm. Like the control arm, a total of 12 packets will be delivered to intervention participants via their method of choice. Since this pilot study seeks to determine the independent effect of the SW-based intervention, SWs will be instructed not to feedback on study-related telephone interactions to the participant's provider. This will be facilitated by the physical separation between the SW offices and the provider work area. Recruitment efforts will also be tailored to inform providers about the study with the minimal amount of details on the intervention available to avoid undue influence on their practice patterns.

All study follow up visits will be conducted within a +/- 21 day window.

